4.3 STUDY TREATMENT AND OTHER TREATMENTS RELEVANT TO THE STUDY DESIGN

The investigational medicinal products (IMPs) for this study are obinutuzumab/placebo and MMF. Prednisone, premedications, and rescue medications are considered non-investigational medicinal products (NIMPs). Appendix 15 identifies all investigational, auxiliary, and non-investigational medicinal products for this study.

Patients may have been taking MMF prior to joining the study given the role of MMF in treatment of proliferative LN as recommended by ACR and EULAR/ERA-EDTA treatment guidelines (Hahn et al. 2012; Bertsias et al. 2012; Fanouriakis 2019). Within the study, MMF will be dispensed for the first time at day of randomization when it will be considered IMP. MMF used prior to Day 1 by the patient will not be considered IMP.

Obinutuzumab and Placebo

Obinutuzumab and placebo will be supplied by the Sponsor as sterile liquid in 50-mL glass vials. For information on the formulation and handling of obinutuzumab/placebo, see the Obinutuzumab Immunology Investigator's Brochure and pharmacy manual.

Mycophenolate Mofetil

MMF will be supplied or reimbursed by the Sponsor. For information on the formulation and handling of MMF, see the local prescribing information.

4.3.1 Study Treatment Dosage, Administration, and Compliance

The treatment regimens are summarized in Sections 3.1.2 and 3.1.3.

Refer to the pharmacy manual for detailed instructions on drug preparation, storage, and administration.

Any dose modification should be noted on the Study Drug Administration electronic Case Report Form (eCRF). Cases of overdose, medication error, drug abuse, or drug misuse, along with any associated adverse events, should be reported as described in Section 5.3.5.12.

Guidelines for treatment interruption or discontinuation, and for resumption, for patients who experience adverse events are provided in Section 5.1.3.

4.3.1.1 Obinutuzumab and Placebo

Obinutuzumab 1000 mg or placebo will be administered by IV infusion during blinded treatment at Day 1 and Weeks 2, 24, 26, 50, and 52 as described in Section 3.1.2. Subsequent blinded infusions will occur at Week 80 and every 6 months thereafter for

patients with an adequate response at Week 76. OLT will follow the initial obinutuzumab treatment schedule with infusions on OLT Day 1; at OLT Weeks 2, 24, 26, 52, and every 6 months thereafter (see Section 3.1.3).

Instructions for the administration of obinutuzumab or placebo infusions are provided in Appendix 6.

4.3.1.2 Mycophenolate Mofetil

All patients will receive MMF from the baseline visit (Day 1) onward. MMF will be titrated by Week 4 to a target dose of 2.0–2.5 g/day in divided doses. For patients newly initiating MMF, the recommended initial dosage is 1.5 g/day given in divided doses with titration by 500 mg/week to 2.0–2.5 g/day by Week 4.

If the investigator believes a patient requires MMF doses in excess of 2.5 g/day, the Medical Monitor should be contacted to discuss whether the target dose should be increased.

MMF should be maintained at the target dose through Week 80. Adjustments to MMF dosing will be permitted because of intolerance and adverse events. The dosage should not exceed 2.5 g/day unless discussed with the Medical Monitor. The guidelines for MMF dosing and recommended dose adjustments are provided in Appendix 7.

After Week 80, background immunosuppression may be adjusted at the discretion of the investigator. Investigators may continue MMF or switch to azathioprine (target dose: 2 mg/kg/day) as permitted by treatment guidelines. These therapies should be provided and monitored in a manner consistent with the ACR and/or EULAR/ERA-EDTA treatment guidelines (Hahn et al. 2012; Bertsias et al. 2012; Fanouriakis 2019), or local clinical practice.

MMF will be provided to the patient for home administration. To assess patient compliance with self-administration of MMF, patients will be required to record the date they took each dose in a medication diary; missed doses will also be recorded. Patients will be instructed to bring all unused study medication and their medication diaries at specified study visits for assessments of compliance.

4.3.2 Additional Medications

4.3.2.1 Corticosteroid Administration

All patients will receive IV and oral corticosteroids for the treatment of LN, consistent with ACR and EULAR/ERA-EDTA treatment guidelines (Hahn et al. 2012; Bertsias et al. 2012; Fanouriakis 2019). Every effort must be made to follow the corticosteroid regimen described below to permit the primary comparison of obinutuzumab and placebo.

Intravenous Corticosteroid Treatment

During the 6 months prior to screening, during screening, or on Day 1 (prior to the first infusion), all patients must have received at least one dose of pulse-dose methylprednisolone IV (250–1000 mg) or equivalent for the treatment of the current episode of active LN. Where possible, pulse corticosteroids should be completed prior to screening. The maximum permitted dose of pulse corticosteroids during the 4 weeks prior to screening or during screening is 3 g methylprednisolone IV or equivalent. If not given during the 6 months prior to screening or during screening, a single dose of pulse-dose methylprednisolone IV (250–1000 mg) will be given in place of pre-infusion methylprednisolone 80 mg IV on Day 1 only (see Section 4.3.2.2).

At blinded obinutuzumab or placebo infusions at Day 1 and Weeks 2, 24, 26, 50, and 52, methylprednisolone 80 mg IV will be given to prevent IRRs (see Section 4.3.2.2). Oral prednisone should not be administered on days when pre-infusion methylprednisolone is given.

Oral Prednisone Treatment

All patients will receive oral prednisone and follow a standardized tapering schedule through Week 80. In regions where prednisone or the specified dose of prednisone is not readily available, an approximately equivalent dose of an oral corticosteroid with a similar duration of action may be substituted (see Appendix 4).

During screening, prednisone may be administered up to 0.5 mg/kg/day (maximum 60 mg/day) if clinically indicated. Oral prednisone should not be administered on all days when pre-infusion methylprednisolone is given.

On Day 2, all patients will receive oral prednisone 0.5 mg/kg/day (maximum 60 mg/day) and remain at this dose until the Week 2 visit. Beginning on Day 15, prednisone will be tapered to achieve a target dose of 5 mg/day by Week 24 according to the schedule in Table 2. Prednisone will be maintained at 5 mg/day from Week 24 until Week 80.

Table 2 Prednisone Tapering Schedule through Week 80

	Prednisone Dose (mg/day) ^a			
Days 2-14	30	40	50	60
Week 2	25	30	40	50
Week 4	25	25	30	40
Week 6	20	20	20	30
Week 8	15	15	15	20
Week 10	10	10	10	10
Week 12	7.5	7.5	7.5	7.5
Weeks 24-80	5	5	5	5

Oral prednisone is started at 0.5 mg/kg/day (maximum 60 mg/day). Starting doses should be rounded to the nearest 10 mg dose or the nearest dose that is feasible based on the locally available oral prednisone dose strengths. An approximately equivalent dose of an oral corticosteroid with a similar duration of action may be substituted.

Corticosteroid Dose Increases

Treatment with higher doses of prednisone is permitted if judged clinically necessary by the investigator for renal and extrarenal flares (see Appendix 5). Use of intravenous corticosteroids during the study is strongly discouraged unless gastrointestinal involvement temporarily precludes the use of oral corticosteroids.

Patients may receive higher doses of corticosteroids for emergent illness or surgery if clinically indicated; the corticosteroid use should be limited to the minimum duration and dose necessary before resuming the prednisone taper.

Use of pulse steroids or sustained, high-dose corticosteroids from Week 64 onward is considered corticosteroid rescue, will result in nonresponse for subsequent efficacy assessments, and should be avoided (see Section 4.4.4.1).

Corticosteroid Treatment after Week 80

After Week 80, the prednisone dose may be adjusted at the discretion of the investigator. Oral prednisone should not be administered on days when pre-infusion methylprednisolone is given.

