Table 1 Prednisone Dosing for Renal and Extrarenal Flares

Weeks after Initial Corticosteroid Increase		Pred	dnisone Do (mg/day)		
	20	30	40	50	60
2	15	25	30	40	50
3	15	20	25	30	40
4	≤10	15	20	20	30
5	≤10	≤10	15	15	20
6	≤10	≤10	≤10	≤10	≤10

^a Oral prednisone may be given at up to 0.5 mg/kg/day (maximum 60 mg/day). Starting doses should be rounded to the closest 10 mg increment or the nearest increment that is feasible based on the locally available oral prednisone dose strengths. An approximately equivalent dose of an oral corticosteroid with a similar duration of action may be substituted if necessary.

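### For patients from 30 kg to under 50 kg, the prednisone start rule with 10 mg rounding leads to a dose that Table 2 does not contain, and the Week 2 and Week 4 rows lie above it

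*Protocol*

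**What the plan says.** Protocol 4.3.2.1 (Corticosteroid Administration) contains three instructions that have to work together.

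- Start dose: "On Day 2, all patients will receive oral prednisone 0.5 mg/kg/day (maximum 60 mg/day) and remain at this dose until the Week 2 visit".
- Rounding, in the footnote to Table 2: "Starting doses should be rounded to the nearest 10 mg dose". As an alternative, the footnote accepts whatever dose comes closest given the tablet strengths that a site can obtain.
- Taper: from Day 15 all patients step down along Table 2 to 5 mg/day by Week 24. The start row reads "Days 2-14 30 40 50 60" and the next row "Week 2 25 30 40 50". The Week 4 row is 25, 25, 30 and 40 mg, and the Week 6 row is 20, 20, 20 and 30 mg.

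The same section gives the reason for a standard regimen: "Every effort must be made to follow the corticosteroid regimen described below to permit the primary comparison" of obinutuzumab with placebo. The eligibility criteria (Protocol 4.1.1 and 4.1.2) set an age range but no minimum body weight. No text says which Table 2 column applies when the rounded start dose is below 30 mg.

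**The concern.** A rule that applies to every patient should lead every eligible patient to a line of the schedule. For light patients it does not. With 10 mg rounding, the start dose falls to the left of the table's first column, and the first two taper steps in every column are higher than that start. The site must then either raise the dose when the taper should begin, or start above 0.5 mg/kg in order to have a column to follow.

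At stake is the dose that these patients receive in about the first six weeks, and how uniform it is in a regimen that the protocol wants standardized. The endpoint that takes in these weeks directly is the exploratory cumulative corticosteroid dose from baseline to Week 76 (Protocol 2.1.3; SAP 1.1.1.3).

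**Working it through.** **Inputs.** All are from Protocol 4.3.2.1: 0.5 mg/kg/day, cap 60 mg/day, rounding to the nearest 10 mg, and the rows of Table 2. The plan gives no figure of its own to reproduce here.

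**Step 1: start dose by weight.** Dose = min(0.5 × weight, 60), rounded to the nearest 10 mg.

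| Weight (kg) | 0.5 × weight (mg) | Rounded (mg) | Column in Table 2? |
|---|---|---|---|
| 30 | 15.0 (tie, rounded up) | 20 | no |
| 35 | 17.5 | 20 | no |
| 40 | 20.0 | 20 | no |
| 45 | 22.5 | 20 | no |
| 49.9 | 24.95 | 20 | no |
| 50 | 25.0 (tie, rounded up) | 30 | yes |
| 60 | 30.0 | 30 | yes |
| 80 | 40.0 | 40 | yes |
| 100 | 50.0 | 50 | yes |
| 120 | 60.0 | 60 | yes |

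From 30 kg to under 50 kg the result is 20 mg, which has no column. Below 30 kg it would be 10 mg, which has none either. From 50 kg upward every rounded dose has a column, taking the exact tie at 50 kg as rounded up.

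**Step 2: a 20 mg start followed by the lowest column.** The sequence is 20 (start), 25 (Week 2), 25 (Week 4), 20 (Week 6), 15 (Week 8), 10 (Week 10), 7.5 (Week 12), 5 (Week 24). The dose rises by 5 mg on the day the taper should begin, and first returns to the start level at Week 6.

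**Step 3: the 30 mg column from the start.** Dose per kg = 30 / weight.

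- 49 kg: 30/49 = 0.61 mg/kg, 22% above 0.5
- 45 kg: 30/45 = 0.67 mg/kg, 33% above
- 40 kg: 30/40 = 0.75 mg/kg, 50% above

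**Step 4: the local-feasibility clause.** Where tablet strengths allow, a patient of 45 to 49.9 kg (22.5 to 24.95 mg calculated) might start at 25 mg. On the lowest column this gives 25, 25, 25, 20, with no reduction at Week 2 or Week 4. The clause changes the start but supplies no taper.

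**Step 5: where the conflict ends.** From Week 6 the 30, 40 and 50 mg columns are identical (20, 15, 10, 7.5, 5). Only the start, Week 2 and Week 4 are in conflict.

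**Step 6: size in cumulative dose.** This is an illustration only; neither line is a proposed regimen, and infusion days without oral prednisone are ignored. Day 2 to Week 6 is 13 + 14 + 14 = 41 days.

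- 30 mg column: 13 × 30 + 14 × 25 + 14 × 25 = 1,090 mg
- Flat 20 mg: 41 × 20 = 820 mg
- Difference: 270 mg, and 270/820 is about one third

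**Step 7: do the later steroid rules see it?** The key secondary taper criterion counts prednisone above 7.5 mg/day from Week 64 through Week 76. Corticosteroid rescue for the primary endpoint also counts from Week 64. SAP 4.2.1.1 applies a 12-week look-back at other response visits. The earliest of these is Week 24, so that window opens at Week 12, when every column is at 7.5 mg. None of these windows overlaps the conflict.

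**The case against.** The strongest reply is that the footnote does not force a 20 mg start. Its second half allows the nearest locally feasible dose, and departures from exactly 0.5 mg/kg are inherent in 10 mg rounding: at 50 kg, rounding the tie up already gives 30/50 = 0.60 mg/kg. This stands in part. A 20 mg start is one permitted outcome and not the only one, and the 22% excess at 49 kg is close to the 20% that the rounding rule itself can produce at 50 kg. But the clause leaves the patient without a column, and at 40 kg the excess is 50%.

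Three stronger readings are tempting, and the documents do not support them.

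- A reader might infer that these patients cannot follow the mandated taper at all. They can from Week 6 onward, and the 5 mg target by Week 24 is reachable.
- A reader might infer that a key secondary endpoint or the rescue rule is affected, because both use steroid dose. Their windows open well after the conflict ends (Step 7).
- A reader might point to Appendix 5, whose flare table has a 20 mg column and a similar footnote ("Starting doses should be rounded to the closest 10 mg increment"), as proof that the protocol expects light patients to start there. Flare doses are allowed up to 0.5 mg/kg, which is a ceiling, so a patient of any weight may start a flare course at 20 mg. The column shows nothing about intent for Table 2.

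Harm to the primary comparison is not shown either. The start dose depends on weight and not on assigned arm, and treatment is randomized and double-blind, so any inconsistency is expected to fall on both arms alike. The documents also do not establish that sites will in fact differ; they only leave the choice open.

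**Conclusion.** The inconsistency is real, minor and narrow. For patients from 30 kg to under 50 kg, no reading that uses 10 mg rounding satisfies both the 0.5 mg/kg start and a Table 2 taper that steps down from it. The conflict covers the start dose and the Week 2 and Week 4 rows only.

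In size, it is either a 5 mg increase at Week 2 or a start that is 22% to 50% above 0.5 mg/kg between 49 and 40 kg. In the Step 6 illustration, two ways of dosing such a patient differ by about 270 mg over the first six weeks.

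The conclusion rests on the absence of a weight limit in the eligibility criteria and on Table 2 really having four columns. Each of its rows carries four values, while the flare table in Appendix 5 has five columns, so a column lost from the text is unlikely. The share of patients under 50 kg is not given, so the effect on the trial as a whole cannot be sized. The primary endpoint definition, the Week 64 to 76 steroid criteria and the sample size are untouched, and a reader should not infer bias between arms. This is an inconsistency in the text and not a disputable design choice.

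**What to change.** The sponsor should reconcile the 0.5 mg/kg rule, the rounding footnote and Table 2 in Protocol 4.3.2.1, so that every eligible body weight maps to one stated taper. The local-feasibility clause should be covered too, by saying which taper applies when the start dose is not a column heading. The content is for the sponsor's clinicians, and no dose or schedule is proposed here.

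The cost is one table or footnote correction in the protocol. The endpoint definitions, the SAP analyses and the sample size need no change. For patients already treated, describing the early prednisone doses actually given to those under 50 kg would show whether the gap mattered in practice.

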4.3.2.2 Premedications

For blinded infusions at Day 1 and Weeks 2, 24, 26, 50, and 52, the following premedications will be administered. The administration of all premedications must be completed between 30 and 60 minutes prior to the obinutuzumab or placebo infusion:

- Methylprednisolone 80 mg IV and
- Acetaminophen (650–1000 mg) orally (PO) and
- Diphenhydramine 50 mg PO or IV (or equivalent dose of a similar agent)

For blinded infusions at Week 80 and beyond, premedication with methylprednisolone will only be given to those patients who experienced an IRR with the previous blinded infusion. Acetaminophen and diphenhydramine will be administered prior to all infusions.

For patients who did not receive the required pulse dose of IV corticosteroids during the 6 months prior to or during screening, a single pulse dose of methylprednisolone IV (recommended: 250 mg; permissible range 250–1000 mg) will be given instead of pre-infusion methylprednisolone 80 mg IV on Day 1 only.

During OLT, all patients will receive premedication with methylprednisolone 80 mg IV through the OLT Week 52 infusion; subsequently, pre-infusion methylprednisolone will only be given to patients who experienced an IRR with the previous obinutuzumab infusion. Acetaminophen and diphenhydramine will be administered prior to all infusions.

Instructions for the administration of premedications are provided in Appendix 6.

4.3.3 Investigational Medicinal Product Accountability

All IMPs required for completion of this study will be provided or reimbursed by the Sponsor where required by local health authority regulations. The study site will acknowledge receipt of IMPs supplied by the Sponsor using the IxRS to confirm the shipment condition and content. Any damaged shipments will be replaced.

IMPs will either be disposed of at the study site according to the study site's institutional standard operating procedure or be returned to the Sponsor with the appropriate documentation. The site's method of destroying Sponsor-supplied IMPs must be agreed to by the Sponsor. The site must obtain written authorization from the Sponsor before any Sponsor-supplied IMP is destroyed, and IMP destruction must be documented on the appropriate form.

Accurate records of all IMPs received at, dispensed from, returned to, and disposed of by the study site should be recorded on the Drug Inventory Log.

4.3.4 Continued Access to Obinutuzumab and MMF

The Sponsor will offer continued access to Roche IMP (obinutuzumab and MMF) free of charge to eligible patients in accordance with the Roche Global Policy on Continued Access to Investigational Medicinal Product, as outlined below.

A patient will be eligible to receive Roche IMP (obinutuzumab and MMF) after completing the study (see Section 3.1.6) if all of the following conditions are met:

- The patient has a life-threatening or severe medical condition and requires continued Roche IMP treatment for his or her well-being
- There are no appropriate alternative treatments available to the patient

 The patient and his or her doctor comply with and satisfy any legal or regulatory requirements that apply to them

A patient will not be eligible to receive Roche IMP (obinutuzumab and MMF) after completing the study if any of the following conditions are met:

- The Roche IMP is commercially marketed in the patient's country and is reasonably accessible to the patient (e.g., is covered by the patient's insurance or wouldn't otherwise create a financial hardship for the patient)
- The Sponsor has discontinued development of the IMP or data suggest that the IMP is not effective for LN
- The Sponsor has reasonable safety concerns regarding the IMP as treatment for LN
- Provision of the Roche IMP is not permitted under the laws and regulations of the patient's country

The Roche Global Policy on Continued Access to Investigational Medicinal Product is available at the following website:

http://www.roche.com/policy_continued_access_to_investigational_medicines.pdf

4.4 CONCOMITANT THERAPY

Concomitant therapy consists of any medication (e.g., prescription drugs, over-the-counter drugs, vaccines, herbal or homeopathic remedies, nutritional supplements) used by a patient in addition to protocol-mandated treatment from 7 days prior to screening to the study completion/discontinuation visit. All such medications should be reported to the investigator and recorded on the Concomitant Medications eCRF. Under certain circumstances, the Medical Monitor may assess that medications used by a patient more than 7 days prior to screening may need to be captured on the Concomitant Medications eCRF (e.g., COVID-19 vaccinations and latent TB treatment must always be captured on the Concomitant Medications eCRF).

4.4.1 Recommended Therapy

4.4.1.1 Antihypertensive Therapy

Patients should receive either an angiotensin-converting enzyme (ACE) inhibitor or an angiotensin-receptor blocker (ARB) titrated to adequate blood pressure control as recommended by the KDIGO (Kidney Disease: Improving Global Outcomes) Blood Pressure Work Group for chronic kidney disease (Becker et al. 2012). Patients should be on either an ACE inhibitor or ARB for at least 10 days prior to randomization. Combination therapy with ACE inhibitor and ARB is not permitted.

During screening, every effort should be made to adequately control patients' blood pressures. The dose of the ACE inhibitor or ARB may be titrated upward to the maximum recommended dose in the current package insert to achieve adequate blood pressure control as recommended by the KDIGO Blood Pressure Work Group (Becker et al. 2012). If adequate blood pressure control is not achieved, patients may be started

on additional antihypertensive agents but not on agents that affect proteinuria (e.g., non-dihydropyridine calcium channel blockers, aldosterone antagonists, direct renin antagonists). Additional agents that specifically target the renin-angiotensin system cannot be initiated during the study. Suggested dose ranges for specific ACE inhibitors and ARBs are listed in Table 3.

ACE inhibitor and ARB therapy exposure during the second and third trimesters is known to induce human fetal toxicity (decreased renal function, oligohydramnios, skull ossification retardation) and neonatal toxicity (renal failure, hypotension, and hyperkalemia). The use of ACE inhibitors and ARBs is not recommended during the first trimester of pregnancy and is contraindicated during the second and third trimester of pregnancy.

If patients are intolerant to ACE inhibitors and ARBs, they may use either a direct renin inhibitor or aldosterone antagonist, but not in combination.

Other antihypertensive agents that affect proteinuria must not be used prior to Week 80 unless discussed with the Medical Monitor. These include non-dihydropyridine calcium antagonists, aldosterone antagonists, and direct renin antagonists.

Table 3 Suggested Dose Ranges for Angiotensin-Converting Enzyme Inhibitors and Angiotensin-Receptor Blockers

ACE Inhibitor or ARB	Dose Range (Oral) (mg/day)	
ACE inhibitors		
Benazepril	10–80	
Ramipril	2.5–10	
Lisinopril	10–80	
Enalapril	10–40	
Quinapril	10–80	
Captopril	75–450	
Perindopril	4–16	
Trandolapril	1–8	
Moexipril	7.5–30	
ARBs		
Eprosartan	400–600	
Valsartan	80–320	
Olmesartan	20–40	
Candesartan	8–32	
Telmisartan	20–80	
Losartan	25–100	
Irbesartan	75–300	

ACE=angiotensin-converting enzyme; ARB=angiotensin-receptor blockers.

